### 8.1 **Primary Analyses**

The primary endpoint analysis will be performed calculating the proportion of patients with active disease at Day 1. The results will be presented as percentage and calculated as:

For Crohn's Disease (CD):

Number of patients with active CD (HBI score  $\geq 8$  or CDAI score  $\geq 220$ )  $p_{CD}$  = Total number of CD patients

## For Ulcerative Colitis (UC):

icable terms of Use Number of patients with active UC  $(9 - point partial Mayo score \ge 5)$ Total number of UC patients

The 95% confidence intervals will be computed for each estimate.

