# Study Administrative Structure

# **Study Sites**

The study is planned to be conducted in approximately 7 sites in Argentina. The selected sites are public and private institutions in Argentina recognized by their large experience in the IBD management, and that follow IBD patients in ambulatory care.

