#### 6.2 **Discussion of Study Design**

This is a non-interventional study, with a cross-sectional evaluation and retrospective chart review, designed to evaluate disease control, treatment patterns, burden of disease and health related quality of life among patients with IBD. The cross-sectional design with no control group is suitable and feasible to address the study objectives, which are mainly descriptive.

In terms of external validity, two major points should be considered. First, the 7 study sites will be selected among reference public and private institutions for IBD management in different districts in Argentina. It is expected that their patients will be representative of patients with moderate to severe IBD in Argentina. In addition, the inclusion and exclusion criteria are not restrictive and will enable the assessment of real-world data about IBD control in Argentina. Internal validity will be reinforced by training of Investigators and the use of same study procedures and forms. Hence, observation bias is not expected to occur during the cross-sectional evaluation. Although retrospective data collection is challenged by the quality of medical records, treatment patterns and hospitalizations are frequently recorded and no significant missing data is expected, which could lead to underestimation of health care utilization data. In addition, it is expected that completeness of medical records will be high in the last 3 years (retrospective period), namely regarding the use of biological treatments (if prescribed).

Because this is an observational study, some limitations should be minimized. All eligible patients will be consecutively invited to the study and the enrolment period will be of at least 6 months. Disease control may be underestimated due to selection bias, since patients with active IBD are expected to have more medical appointments and thus, may be have more frequent visits to the center. Nevertheless, the 6-month period will also enable the inclusion of patients with mild or no active disease (although, for the same reason, these patients may be underestimated).

Potential confounders will be addressed at:

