### 2.2 Endpoints

### **Primary endpoints** 2.2.1

- For Crohn's Disease: Proportion of patients with active disease (HBI score  $\geq 8$ or CDAI score  $\geq$  220 points - based on criteria used by the site) at Day 1.
- For Ulcerative Colitis: Proportion of patients with active disease (9-point partial Mayo score ≥5) at Day 1.

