This is a multicenter, non-interventional, cross-sectional study (Figure 1) aiming primarily to determine the rate of control of IBD activity (Crohn's Disease [CD] or Ulcerative Colitis [UC]). At each center, eligible subjects will be identified consecutively as they attend a scheduled clinical appointment with their physician (Day 1). Upon written consent, data regarding disease activity, treatment patterns, burden of disease and quality of life will be collected from the patients' medical records and administered Patient Report Outcome (PRO) questionnaires, including quality of life (SF-36, EQ-5D and IBDQ) and work productivity (WPAI) questionnaires. Besides the cross-sectional data collection, the study will have an additional retrospective data collection referring to the three years previous to Day 1, regarding the previous IBD treatments (drug, dose, treatment duration and drug changes), and use of other healthcare resources related with the management of IBD. Property of

Day 1

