### 5 PROTOCOL CLARIFICATIONS

The last secondary objective, estimation of healthcare resources cost, will not be calculated as stayed in section 3 of the protocol (3. Study objectives), since these variables were not The of Use collected in the CRF.

Adverse events were not collected in the study database and results regarding these variables will not be presented in the statistical report.

Secondary endpoint "Proportion of patients who guit their job due to IBD and have not been able to return to work" will not be calculated as stayed in section 10.1.1 of the protocol (10.1.1 Study endpoints), since these variables were not collected in the CRF

In the protocol the analysis dataset was not defined. In this SAP the analysis dataset was defined according to section 6 Definition of analysis subsets.

The descriptive analysis for continuous variables will be summarized by mean, standard variation, median, maximum, minimum as stayed in the protocol and also by first quartile and third quartile.

## 6

DEFINITION OF ANALYSIS SUBSETS only and Analysis dataset - All patients fulfilling selection criteria (section 4), who provided the written informed consent, without major study protocol deviations and who have completed the Day 1 assessment will be included in the statistical analysis dataset.

### RATIONALE AND CALCULATION OF THE SAMPLE SIZE 7

It is expected to include 246 patients regardless of IBD type.

This sample size will allow estimates with 95% confidence interval and a margin of error less than 5%, and assuming a rate of inadequate control of disease of 20% (conservative approach), regardless of IBD type. The following formula was used:

$$n = \frac{1.96^2 \times p \times (1-p)}{ME^2}$$

Rate of uncontrolled disease (p) = 20%

Margin of error (ME) = 0.05

Expected recruitment period: 6 months

ofUse

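### The primary confidence intervals and the 5% margin make no allowance for recruitment at about 7 sites; if activity rates differ between sites, simple binomial intervals will be too narrow.

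*SAP*

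**What the plan says.** **Analysis.** SAP 8.1 and protocol 10.2 divide the number of patients with active disease by the number of patients, once for CD and once for UC. On intervals, SAP 8.1 adds only: "The 95% confidence intervals will be computed for each estimate". No interval method is named. Protocol section 10 and SAP sections 7 to 9 contain no site term, cluster variance or design effect.

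**Sample size.** Protocol 10.6 and SAP 7 use the single-proportion formula with p = 20% and a margin of 0.05. They arrive at 246 patients with CD and UC taken together, and promise "a margin of error less than 5" percent.

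**Sites.** Protocol 4.1 plans "approximately 7 sites in Argentina". Patients are enrolled consecutively within each centre (protocol 6.3.3, SAP 3). Protocol 6.2 says that "the 7 study sites will be selected among reference public and private institutions for IBD management in different districts in Argentina", and then states: "It is expected that their patients will be representative of patients with moderate to severe IBD in Argentina".

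**Measurement.** Active CD is judged on the HBI or the CDAI, "based on criteria used by the site" (SAP 2.2.1). UC is judged on one index, the partial Mayo score.

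**The concern.** Patients seen at the same centre share referral patterns, access to treatment and assessing physicians, so their activity status may be more alike than that of patients from different centres. When results are generalised beyond the recruiting centres, as protocol 6.2 does, that similarity is part of the sampling error. A formula for independent patients leaves it out.

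The primary result of this study is a proportion with its interval, so the width of that interval is central. With few sites and many patients at each, even a small correlation matters. It would mean that a nominal 95% interval covers less often than stated, and that the design does not deliver the advertised margin.

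**Working it through.** **Inputs from the documents:** N = 246, p = 0.20, margin 0.05, z = 1.96 (protocol 10.6, SAP 7); about 7 sites (protocol 4.1).

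**Assumptions, because the documents give no figure:** ICC between 0.01 and 0.05; 7 sites of equal size; 123 patients per disease. At p = 0.20, these ICCs correspond to a between-site standard deviation of √(0.16 × 0.01) = 4 points to √(0.16 × 0.05) = 9 points.

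**Step 1: the plan's own figure.** n = 1.96² × 0.20 × 0.80 / 0.05² = 245.86, rounded up to 246. This reproduces. The margin at 246 is 1.96 × √(0.16/246) = 4.999 points. Any positive ICC therefore takes the pooled margin above 5 points.

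**Step 2: allow for site.**
- Patients per site: m = 246/7 = 35.1 pooled; 123/7 = 17.6 per disease.
- Design effect: DE = 1 + (m − 1) × ICC.
- Margin: 1.96 × √(0.16 × DE / N). With t on 6 df (7 sites minus 1), the t value replaces 1.96.
- Coverage of an interval that ignores site: 2Φ(1.96/√DE) − 1.

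Example, one disease, ICC 0.05: DE = 1 + 16.57 × 0.05 = 1.83; margin = 1.96 × √(0.16 × 1.83/123) = 9.6 points; coverage = 2Φ(1.45) − 1 = 85%.

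| Sample | ICC | DE | Effective n | Margin, z | Margin, t (6 df) | Coverage of simple interval |
|---|---|---|---|---|---|---|
| Per disease, 123 | 0 | 1.00 | 123 | 7.1 | 8.8 | 95% |
| Per disease, 123 | 0.01 | 1.17 | 105.5 | 7.6 | 9.5 | 93% |
| Per disease, 123 | 0.02 | 1.33 | 92.4 | 8.2 | 10.2 | 91% |
| Per disease, 123 | 0.05 | 1.83 | 67.3 | 9.6 | 11.9 | 85% |
| Pooled, 246 | 0 | 1.00 | 246 | 5.0 | 6.2 | 95% |
| Pooled, 246 | 0.01 | 1.34 | 183.4 | 5.8 | 7.2 | 91% |
| Pooled, 246 | 0.02 | 1.68 | 146.2 | 6.5 | 8.1 | 87% |
| Pooled, 246 | 0.05 | 2.71 | 90.9 | 8.2 | 10.3 | 77% |

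The primary proportions are per disease, so the upper half of the table is the relevant one for them. The lower half speaks to the promised 5% margin.

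**Step 3: how far the assumptions matter.**
- *Split by disease.* The only UC to CD ratio in the documents is 7.04:1, from one city (protocol section 2). If it applied here, CD would have 246/8.04 = about 31 patients and UC about 215. For ICC 0.01 to 0.05, coverage would be 94.6% to 93.0% in CD and 91.5% to 78.6% in UC.
- *Unequal sites.* With a coefficient of variation of site size of 0.5, DE = 1 + (1.25 × m − 1) × ICC. The pooled margin is then 6.0 points at ICC 0.01 and 8.9 at 0.05.
- *More patients.* With sites fixed at 7, a pooled 5-point margin needs N = 245.86 × (1 − ICC) / (1 − 245.86 × ICC/7). That is 376 patients at ICC 0.01 and 810 at 0.02. At 0.05 the denominator is negative, so no N suffices.

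**The case against.** **The interval method is not stated, and no ICC is given.** A reader might infer that the planned intervals are bound to undercover. The documents do not support that. Independence is the natural reading of a simple proportion beside this formula, but SAP 8.1 does not say so. Undercoverage also needs activity rates that differ between sites. At ICC = 0 the objection disappears. This stands, and the point is therefore conditional.

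**The sites were chosen, not sampled.** If inference is confined to these centres, a binomial interval is defensible for a mainly descriptive study, and no cluster variance makes chosen reference centres representative. The second half stands. The first is hard to square with the national target in protocol 6.2.

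**The pooled figures overstate the loss on the primary intervals.** Coverage as low as 77% belongs to the pooled sample. For the per-disease estimates the corresponding figure is about 85% at an assumed 123 patients each. This stands.

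**The site-dependent index does not prove correlation.** A reader might infer that the choice between HBI and CDAI builds it into the measurement. That choice exists for CD only, and nothing shows that the two cut-offs give different activity rates. If they do, the problem is comparability, which a wider interval does not cure. SAP section 9 already derives which index or indices each CD patient had. The index is a possible source of between-site variation, no more.

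**The logistic models do not exclude site.** SAP 8 admits variables on clinical grounds, at p<0.200, or at the sponsor's request. Site is not named, but it could enter. A random intercept over 7 sites with about 0.20 × 123 = 25 active cases per disease would be fragile. This stands. The table shells are a separate document not available here, so by-site tables may already be planned.

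**Conclusion.** The concern holds in conditional form. The 246 patients and the 5% margin rest on independence, and neither document allows for site in the sample size or in the primary intervals, while protocol 6.2 generalises to Argentina. If activity rates differ between sites, simple binomial intervals will be too narrow. For ICCs of 0.01 to 0.05 the loss on the primary estimates runs from slight (93% coverage, 0.6 points added to the margin) to material (85%, 2.5 points added). These figures rest on an assumed ICC, equal sites and an even split by disease.

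A separate matter should not be charged to clustering: the 5% margin is for the pooled sample, and at 123 per disease the margin is already 7.1 points under independence.

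**What to change.** 1. **SAP 8.1:** name the binomial interval method. For each of CD and UC, report beside it a site-clustered 95% interval as a sensitivity analysis, for example PROC SURVEYFREQ with site as the cluster and sites minus 1 degrees of freedom.
2. **SAP 8.1:** tabulate the proportion with active disease by site, and for CD also by index used.
3. **SAP 7:** state that the 5% margin holds only for the pooled 246 patients under independence, and show the per-disease and clustered margins for a range of ICCs.
4. **SAP 8.2:** where the number of active cases allows, repeat the logistic models with site included, as a sensitivity analysis. A random intercept need not be mandated.

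**Cost:** wording and a few tables. Protocol 9.4 already has the site identifier in the database, SAS 9.4 is the planned software, and SAP section 1 provides for documenting changes in the statistical report. The clustered intervals will generally be wider, partly because of the t value on 6 df: even at ICC = 0 the per-disease margin goes from 7.1 to 8.8 points. A variance estimated from 7 sites is itself imprecise, which is why both intervals should be shown.

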### **Secondary Analyses** 8.2

The following objectives will be addressed for all IBD patients:

- In order to characterize socio-demographic and clinical aspects of moderate to severe IBD, a summary table with the descriptive statistics of the selected variables, by CD and UC patients.
- Descriptive statistics will also be used to summarize treatment patterns for CD and UC in the previous 3 years, including the use of biologic therapies and failure to these therapies (if any), time between IBD diagnosis and initial treatment, first treatment after diagnosis of moderate to severe IBD, among other variables of interest.
- Within CD and UC groups, the patients with moderate to severe disease activity will be compared with patients with mild or no activity, regarding socio-demographic, clinical and treatment variables of interest:
  - o Chi-square or Fisher exact tests will be used to compare qualitative variables, such as gender, smoking habits, professional status, family history of IBD, steroid behavior (dependent/refractory), previous treatment with biologic therapies, and previous surgery for IBD, among others.
  - The t-student or Mann-Whitney tests will be used for comparison of quantitative variables, such as age, time since diagnosis, and duration of treatment, among others.

 $\infty$  If applicable, logistic regression models (for CD and UC patients) will be used to identify independent variables associated with disease control at Day 1, and odds ratios (OR) with 95% CI will be presented.

For each IBD disease, a descriptive statistical analysis will be used to summarize patients' QoL (Quality of Life), overall and according to disease activity

• The score of EQ-5D analog scale and responses to each item (Mobility, Selfcare, Usual activity, Pain/discomfort, Anxiety/depression):

- Utilities will be configured such that 0 is associated with being dead and 100 is associated with perfect health; thus, a higher utility value is considered better. Mean (SD) utility index will be estimated for CD and UC patients, overall and according to disease activity.
- The SF-36 uses 36 items to evaluate eight health dimensions (Physical functioning, Role Physical, Body pain, General health, Vitality, Social Functioning, Role-Emotional, Mental Health) and based on standardized scores, two summary scores are to be estimated (Physical Component Score and Mental Component Score). The standard scoring method for SF-36 questionnaire will be obtained using the QualityMetric Health Outcomes™ Scoring Software 4.5 provided by QualityMetric Incorporated.
- The IBDQ score and each of the four IBDQ domains (Bowel systems, Emotional health, Systematic systems and Social function). Total IBDQ score range from 32 to 224, with a higher score reflecting better quality of life. Response to each of the questions is graded from 1 to 7 ("1" being the worst situation and "7" the best). Please see section 9. *Data, derivations and transformations* for the IBDQ scores calculation. Note: The IBDQ is not validated for patients with ostomies and therefore should not be applied for these patients.
- The comparison of SF 36 scale scores or component summary scores, EQ-5D VAS scale and IBDQ domain scores or total score according to disease activity will be performed through the t-test for independent samples or Mann-Whitney test in case of non-normality of the quantitative variable distribution. The association between each EQ-5D dimension and disease activity will be determined for each IBD type using Chi-Square Test.

- o To evaluate the work productivity impairment (WPAI) experienced by moderate to severe IBD patients, the following variables will be estimated and summarized, by CD or UC, overall and according to disease activity. In brief, the WPAI questions are: 1) if currently employed, 2) hours missed due to disease, 3) hours missed other reasons, 4) hours actually worked, 5) degree disease affected productivity while working, 6) degree disease affected regular activities. Percent total work productivity impairment due to IBD (TWPI) defined as the mean of subjects total percentage of work impairment associated with IBD that results from both absenteeism and presenteeism will be calculated for each IBD type. Also percent work time missed due to IBD, percent impairment while working due to IBD and percent total activity impairment due to IBD will be calculated. Please see section 9. Data, derivations and transformations for the percentages' calculation formula. Additionaly, the proportions of patients reporting some absenteeism, some work impairment and some activity impairment due to IBD will be presented. Patients with moderate to severe disease will be compared with patients with no or mild disease regarding WPAI data (percent total work productivity impairment due to IBD, percent work time missed due to IBD, percent impairment while working due to IBD and percent total activity impairment due to IBD) through the t-test for independent samples or Mann-Whitney test in case of non-normality of the quantitative variable distribution
- Healthcare resources (previous 3 years) will be described by IBD group and by disease activity, for the following events: drug therapies, number and type of imaging and laboratory testing, surgeries, number, reason and duration of hospitalizations, number and type of consultations with gastroenterologists or other medical.

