# 6.4 Treatments

### 7 Conduct

# 7.1 Data collection overview

Non-interventional study – no treatments/pharmacotherapy are predefined in the protocol.				
All clinical decisions will be full responsibility of the investigator.				
7 Conduct		by are predefined in the protocol. estigator.		
7.1 Data collection overview		icalor.		
Table 1. Study Flow Chart		200		
Study variables	Day 1	Retrospective data Collection data points approximately 3 years		
Timing of data collection	Day 1 visit	During visit		
Informed consent	Х	SUP		
Inclusion criteria	Х			
Exclusion criteria	x	 >		
Socio-demographic variables				
Smoking habits	у SS х			
Anthropometric Information (Weight, Height, BMI)	Х	Х		
IBD type (CD or UC)	Х			
Date of diagnosis of CD or UC (based on medical records)	Х			
Date and criteria of diagnosis of moderate to severe CD or UC (based on medical records)	Х			
Steroid behavior	Х			
Family history of IBD	Х			
Medical history / Comorbidities	Х	Х		
Disease activity: CD (HBI score or CDAI); UC (partial/total Mayo Score)	Х	Х		
Clinical Characterization of Disease: location, behavior, EIM	Х			
SF-36	Х			

Study variables	Day 1	Retrospective data Collection data points approximately 3 years	C.C.
EQ-5D	Х		پ رې ت
IBDQ**	Х		rms of Use
WPAI	Х		
Previous treatments or regimens 	Х	X	
Treatment started at Day 1 (if applicable)	Х	ADIT	
Previous surgeries for IBD		x pilo	
IBD-related hospitalizations		x	
Previous medical appointments related with IBD management			
Previous CDAI, HBI, Mayo score (when available)		x CC	
Previous calprotectin levels and colonoscopy (when available)		d sulla x	
Other previous imaging, laboratory (including PCR) and histology testing (when available)	All'	X	

 Excludes new treatments prescribed at Day 1 visit.

\*\* Not applicable for patients who have a colostomy or ileostomy ercial U

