### Treatment

- Previous treatments regimens (aminosalicylates, steroids, immunomodulators, or immunossupressors, biologics, probiotics, antibiotics); start date; end date, dose, reason for discontinuation;
- First treatment after diagnosis of moderate to severe IBD (name, dose); andsul
- Treatment started at Day 1 (name, dose);
- Previous surgeries for IBD.

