### 2.2.2 Secondary endpoints

- Distribution of age, gender, smoking habits, professional status, family history, educational level, subject income by IBD type.
- Distribution of clinical variables (steroid behaviour, anthropometric information, medical history and comorbidities, clinical characterization of disease) by BD type.
- Therapies for IBD (aminosalicylates, steroids, immunomodulators, immunosupressors biologics, antibiotics, probiotics and surgeries) and the length of these therapies during the previous 3 years. Property of Taked

Proportion of biologic-experienced patients.

Proportion of patients who have not responded previously to biologic therapies and reason.

- IBD treatment introduced at Day 1 (if applicable).
- Socio-demographic, clinical and treatment-related variables in patients with moderate to severe activity of CD (HBI score  $\geq$  8 or CDAI score  $\geq$  220 points) versus patients with mild or no activity (HBI score < 8 or CDAI score < 220 points).

- Socio-demographic, clinical and treatment-related variables in patients with moderate to severe activity of UC (9-point partial Mayo score ≥5) versus patients with mild or no activity (9-point partial Mayo score <5).
- Mean score of EQ-5D by IBD type.
- Mean score of different components of SF-36 by IBD type.
- Mean total score of IBDQ and by domain (bowel symptoms, systemic symptoms, emotional function and social function). Patients with ostomy will a in the applicable not be evaluated since this questionnaire is not validated to be used in this population.
- Mean total percentage of work impairment (WPAI).
- Mean work time missed (WPAI).
- Mean impairment while working (WPAI).
- Mean total activity impairment (WPAI).
- Healthcare resources (previous 3 years): drug therapies, imaging and laboratory testing, surgeries, hospitalizations and consultations. y and sul

### STUDY DESIGN 3

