## 8 STATISTICAL METHODS

For each study endpoint, data will be summarized for total IBD patients and by IBD type (CD and UC).

Statistical analysis will allow a characterization of the study population, the estimation of primary endpoints and to compare the subgroup of patients with mild or no activity of disease and those with moderate to severe activity. A descriptive analysis will be obtained for all relevant variables, with absolute and relative frequency for categorical variables and mean, standard variation, median, maximum, minimum, first quartile and third quartile, for continuous ones. For each study endpoint, data will be summarized by IBD type (CD or UC). Hence, for each IBD type, the patients with disease activity will be compared with patients with mild or no activity regarding socio-demographic, clinical and treatment variables of interest. The variable normality assumption will be tested using the Kolmogorov-Smirnov test or Shapiro-Wilk test as applicable. Non-parametric tests will be used whenever the assumptions for parametric tests are not accepted. Chi-square or Fisher exact tests will be used to compare activity vs non-activity regarding qualitative variables and t-student / Mann-Whitney tests will be used for comparison of quantitative variables. If applicable, logistic regression will be used for evaluating associated variables. Variables with clinical significance or statistical significance (p<0.200) will be included in the initial logistic regression model, or otherwise specified by the sponsor. All tests will be two-sided considering a significance level of 5%.

Data analysis will be performed using SAS® (version 9.4; SAS Institute Inc, Cary, USA).

There will be no imputation of missing data for this study, unless otherwise specified.

In case of complete missing dates, date is to be considered as missing.

In case of partial dates:

Missing day is to be considered as the 15th day of the month;

• Missing day and month are to be considered as the 1st day of July.

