Yes – Patients with at least one IBD treatment (just IBD class of salicylic derivates, corticosteroids, immunosuppressors or biologic therapy) with end date equal to Day 1 date and reason for end of IBD treatment classified as "Dose changed".

No – Patients without any IBD treatment (just IBD class of salicylic derivates, corticosteroids, immunosuppressors or biologic therapy) with end date equal to Day 1 date and reason for end of IBD treatment classified as "Dose changed".

Total number of IBD treatments during retrospective period (previous 3 years and at Day 1) per patient – Sum of IBD treatments reported during retrospective period (3 years) for each patient in the previous 3 years and including IBD treatment starting at Day 1.

**IBD treatment duration** – Time between the beginning of the IBD treatment until the end of the treatment (in months). For patients with ongoing IBD treatment at Day 1, stop date will be considered as Day 1 date visit.

**Salicylic derivates treatment duration per patient** – Sum of all IBD salicylic derivate treatments duration for each patient (in months). If the patient has two IBD salicylic derivate treatments taking in simultaneous, it will only be considered the treatment with the longest duration.

**Corticosteroids treatment duration per patient** – Sum of all IBD corticosteroid treatments duration for each patient (in months). If the patient has two IBD corticosteroids treatments taking in simultaneous, it will only be considered the treatment with the longest duration.

IS OF USE

Immunosuppressors treatment duration per patient - Sum of all IBD immunosuppressor treatments duration for each patient (in months). If the patient has two IBD immunosuppressors treatments taking in simultaneous, it will only be considered the treatment with the longest duration.

Biologic therapy treatment duration per patient - Sum of all IBD biologic therapy treatments duration for each patient (in months). If the patient has two IBD biologic therapies taking in simultaneous, it will only be considered the treatment with the longest duration

Antibiotics treatment duration per patient - Sum of all IBD antibiotic treatments duration for each patient (in months). ,ct to

Nutritional support treatment duration per patient - Sum of all IBD nutritional support snd treatments duration for each patient (in months).

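### The SAP's treatment duration is neither exposure within the three-year look-back nor complete treatment length, and it is tested between activity groups without censoring

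*SAP*

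**What the plan says.** The endpoint in SAP 2.2.2 (also Protocol 10.1.1) lists the therapies for IBD "and the length of these therapies during the previous 3 years". This is a quantity inside a fixed look-back.

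The derivation in SAP section 9 is different. IBD treatment duration is "Time between the beginning of the IBD treatment until the end of the treatment (in months", followed by the rule "For patients with ongoing IBD treatment at Day 1, stop date will be considered as Day 1 date visit". Nothing cuts a course at the start of the three-year window. The per-class values are sums of these durations; for biologics, for example, "Sum of all IBD biologic therapy treatments duration for each patient (in months".

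SAP 8.2, like Protocol 10.3, compares moderate-to-severe with mild or no activity within CD and UC. It assigns the t-test or Mann-Whitney test to "comparison of quantitative variables, such as age, time since diagnosis, and duration of treatment, among others", two-sided at 5%. Neither document's text marks ongoing courses as censored or plans a Kaplan-Meier or log-rank analysis of treatment duration. The table shells are an external file and cannot be checked.

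Two further passages bear on the repair. Protocol 7.2 lists the data collected for previous treatments: "start date; end date, dose, reason for discontinuation". The footnote to previous treatments in the Protocol 7.1 flow chart reads "Excludes new treatments prescribed at Day 1 visit"; the SAP duration rule does not repeat that exclusion.

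**The concern.** For an ongoing course the SAP value is simply the time since it was started. A drug begun six months ago and still taken therefore scores the same as one abandoned after six months. For a course begun before the look-back, the value includes months that the endpoint does not ask for. One number thus carries two different departures, and the label *duration of treatment* does not tell the reader which quantity was estimated.

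At stake is the reading of the secondary treatment-pattern results. If active patients changed treatment more recently, they will show shorter durations even when persistence is the same in both groups. SAP section 8 also admits variables with p<0.200 to the initial logistic model for disease control, so a start-timing effect could reappear there as an odds ratio for treatment duration.

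**Working it through.** **1. The plan's own figure.** The only design figure is the sample size: 1.96² × 0.20 × 0.80 / 0.05² = 245.86, so 246. It reproduces. It is used here only for plausible group sizes: an even CD/UC split (assumed) gives 123 per type, and 20% active gives 24.6, so 25 versus 98.

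**2. Three quantities for one course.** Let S be months from start to Day 1 and T the complete length.
- SAP value: min(T, S)
- Exposure in the look-back: min(S, 36) − max(S − T, 0)
- Complete duration: T

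| Hypothetical course | SAP | In window | Complete |
|---|---|---|---|
| Started 60 months ago, ongoing | 60 | 36 | over 60 |
| Started 6 months ago, ongoing | 6 | 6 | over 6 |
| Started 30 months ago, stopped after 6 | 6 | 6 | 6 |
| Started on Day 1, ongoing | 0 | 0 | over 0 |

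The first row shows the excess over the endpoint. The second and third show unlike courses receiving the same value.

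**3. Average size.** Assumptions: T exponential with mean m = 24, S uniform over 0 to 120 months, and a course counted if it overlaps the last 36 months. All integrals below are divided by the same factor of 120, which cancels.
- Weight of courses begun in the window: 36. Begun earlier: 24(1 − e^−3.5) = 23.28. Total 59.28, so 23.28/59.28 = 39% began before the window.
- In-window months: [24×36 − 24²(1 − e^−1.5)] + 23.28 × 24(1 − e^−1.5) = 416.5 + 434.0 = 850.5, and 850.5/59.28 = 14.3.
- Months before the window: 24²[1 − 4.5e^−3.5] = 497.7. SAP mean: (850.5 + 497.7)/59.28 = 22.7.
- Complete mean: (864 + 497.7 + 24 × 23.28)/59.28 = 32.4.

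Other means, same assumptions:

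| m | SAP | In window | Complete |
|---|---|---|---|
| 12 | 12.0 | 9.0 | 15.0 |
| 24 | 22.7 | 14.3 | 32.4 |
| 36 | 30.6 | 17.8 | 48.8 |

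If instead every course began inside the 36 months, the SAP value equals in-window exposure: 24 − (24²/36)(1 − e^−1.5) = 11.6 months, with 52% ongoing. The shortfall is then only against complete duration.

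**4. The group comparison.** Simulation with 25 versus 98 patients, one course each, the same exponential persistence in both groups, 4,000 runs per row, nominal 5%. Starts are uniform over the stated months before Day 1. Rejection rates for m = 24:

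| Start window, active / non-active | Mann-Whitney | t-test | Log-rank, censored at Day 1 |
|---|---|---|---|
| 36 / 36 | 5% | 5% | 5–6% |
| 24 / 36 | 18% | 25% | 5% |
| 18 / 36 | 51% | 72% | 5% |
| 12 / 36 | 96% | 100% | 5% |

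Repeat runs of the 18/36 row put Mann-Whitney between 51% and 53%. At m = 12, Mann-Whitney rejects 9%, 21% and 63% for the three unequal rows.

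**5. Splitting completed from ongoing courses.** In the 18/36 scenario at m = 24, Mann-Whitney on completed courses alone rejects about 22–23%, and on ongoing courses alone 51–53%. Splitting does not remove the start-timing effect.

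**Limits.** Step 4 has no course begun before the window, so it does not exercise delayed entry, and it does not reproduce the SAP's summing of several courses per patient.

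**The case against.** The strongest reply is that the endpoint is length within the previous three years. That is fully observed at Day 1, so stopping there is right and nothing is censored. If active patients began later, their exposure before Day 1 really is shorter, and a test that finds this is not a false positive. The analysis is secondary, Protocol 10.5 calls all analyses descriptive, and the external shells may show counts of ongoing courses.

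Much of this stands. A reader might infer that reported durations are simply too short. The documents do not support that: against the endpoint, the missing cut at the window start makes them too long, and they are short only against complete duration. A reader might also infer that the activity comparison has an inflated error rate as planned. That needs a difference in start timing, about which the documents give nothing; with equal timing the planned tests hold about 5%. Nor do the documents support a large shortfall such as 11.6 against 24 months, because that assumes no course began before the window, while Protocol 6.3.1 sets a minimum time since diagnosis and no maximum.

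What the reply does not answer is that the SAP does not compute the endpoint it appeals to. The derivation runs start to end with only the Day 1 limit, and the result is tested as duration of treatment.

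**Conclusion.** The point holds as a mismatch between endpoint, derivation and test. The derived value equals the stated endpoint only when no course began before the window, and equals complete duration only when no course is ongoing. In the illustration with mean 24 months and starts over 120 months, it is 8.4 months above in-window exposure (22.7 − 14.3) and 9.7 below complete duration (32.4 − 22.7). Read as a comparison of persistence, it is distorted only if start timing differs between active and non-active patients; rejection of about 52% rests on windows of 18 versus 36 months, 25 versus 98 patients and one course each. These sizes are conditional, since start dates, true durations and the share ongoing are not given. The effect is confined to secondary analyses. The change is worth making because it settles what those results mean at little cost.

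**What to change.** In SAP sections 8.2 and 9:

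1. For the endpoint, cut every course at both the window start and Day 1 before summing, and label the result *months of exposure in the 3 years up to Day 1*.
2. If persistence is reported or compared, use Kaplan-Meier and log-rank per class and IBD type, with ongoing courses censored at Day 1 and delayed entry for courses begun before the window. Do not describe the exposure test as a difference in treatment duration.
3. Report the number of ongoing courses by activity group. State that courses started at Day 1 are left out of durations, in line with the flow-chart footnote.

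Do not substitute separate tests of completed and ongoing courses.

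The cost is SAP wording and one extra summary per class. Start date, end date and reason for discontinuation are already collected. Delayed entry assumes that the true start date is recorded for courses begun before the window, which should be confirmed against the CRF.
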